In the proposed study, individuals with chronic low back pain (CLBP; n=286) will be assigned randomly to MT or SMT. For both MT and SMT, treatment will consist of 8 weekly, 60-90 min individual sessions. Self-report mechanism and outcome variables will be assessed at baseline, 1-day after each weekly session (via phone by research staff blind to condition or online by the patient), and at 3- and 6-mo follow-up. Spinal stiffness will be assessed for both conditions prior to and after each session. Endogenous opioid (EO) function and conditioned pain modulation (CPM) will be assessed for both conditions at each laboratory session. Specific mechanism factors were chosen to match the theoretical bases of each treatment. Mindfulness will be the specific mechanism for MT because (a) it is a key psychological factor targeted by MT and (b) preliminary research points to mindfulness as a viable mediator of psychological treatments. Spinal stiffness will be the specific mechanism for SMT because (a) it is a mechanical marker that can be measured and (b) changes in spinal stiffness have been shown to mediate treatment effects. Non-specific mechanisms will include changes in (a) CPM assessed via quantitative sensory testing (QST) methods; (b) EO function; (c) pain self-efficacy and catastrophizing; (d) patient expectations of benefit and quality of the therapeutic relationship. We will assess outcomes following published Initiative on Methods, Measurement, and Pain Assessment in Clinical Trials (IMMPACT) recommendations. Pain interference (i.e., reported degree of interference in daily activities that is attributed to chronic pain) will be the primary outcome as it is equally relevant to both treatments, and given findings that reduction in pain intensity is not a primary focus of MT. Secondary outcomes will be pain intensity, mood, pain medication use, and use of pain-related healthcare.

Interventions and Duration

Mindfulness Training (MT)

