6.2.5 Follow-up Visits

Follow-ups 3-month & 6-month (Visits 14 & 15)

- Pain interference (primary outcome), pain intensity, negative affect (anger, anxiety, depression), physical function, sleep disturbance and social support will be assessed via PROMIS item banks.
- Pain catastrophizing will be assessed with the Pain Catastrophizing Scale.
- Mindfulness will be assessed with the Five Facets of Mindfulness Questionnaire (short form), and the Multidimensional Assessment of Interoceptive Awareness (short form).
- Self-efficacy will be assessed with the Pain Self-Efficacy Questionnaire.
- Bothersome pain and attitudes on changing pain (Pain Stages of Change Questionnaire) will also be assessed.
- Assessment of any adverse events.

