9.5.2 Secondary Outcomes

Secondary outcomes are pre-post treatment changes in mindfulness and spinal stiffness (specific mechanisms), and in CPM, pain-related cognition and therapy factors (non-specific mechanisms). Other secondary outcomes refer to pre-post changes in patient reported clinical status. These are pain intensity, negative affect (anger, anxiety, depression), physical function, sleep disturbance and social support assessed via PROMIS item banks.

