9.6 Data Analyses

Primary analyses will be conducted on an ITT basis.

Aim 1: To determine the degree to which MT and SMT produce effects in nonspecific mechanisms.

The primary analyses will employ the two-sample t-test to compare mean change in each nonspecific mechanism within a noninferiority test construct to compare mean change in outcome from pre to post treatment between the two treatment arms. An overall, 2-sided, significance level of 0.05 will be used. Linear mixed models will be used as a supplemental analysis, allowing us to utilize all data collected, account for within subject variation, and model changes over time. The fixed effect part of the model will be

$Mechanism_{ij} = \beta_0 + \beta_1 Time_{ij} + \beta_2 Tx_i + \beta_3 (Tx_i * Time_{ij}) + \varepsilon_{ij}$ for subject i at visit j.

If β_3 is significantly negative ($p < .05$), this would indicate that the mechanism variable decreased more in SMT than in MT (Fitzmaurice, Laird, & Ware, 2011). In case of a significant interaction, we will test simple slopes of Time for each Treatment Condition separately AND by testing post treatment differences between MT and SMT controlling for pre-treatment values.

Candidate covariance structures will be assessed using the data's correlation structure and Akaike's Information Criterion (AIC). Random coefficients (e.g. random intercept and/or random slope) will be included in the model if they significantly improve the model fit as determined by the likelihood ratio test. Standardized residuals and Cook's distance will be used to assess the influence of outliers and individual observations. Residual plots will be used to check the multivariate normal distribution assumption. The pattern of missing data will be examined to determine its missing mechanism and the amount. If data are missing not at random (MNAR), data imputations may be used. If other deviations from the model assumptions are detected, appropriate measures will be taken to prevent inferential bias, e.g. data transformations and use of bootstrap techniques to compute standard errors.

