Potential covariates (site, age, and any baseline variables found to be significantly different ($p < .20$) between treatment groups) will be considered for model inclusion using a model selection method called least absolute shrinkage and selection operator (LASSO) (Tibshirani, 2011). This method identifies groups of covariates to form a parsimonious model; it avoids problems in stepwise procedures such as collinearity, bias, and variance deflation (Flom & Cassell, 2007); the method has recently been extended to mixed effects models (Bondell, Krishna, & Ghosh, 2010; Fan & Li, 2012; Fernandez, 2007).

Aim 2: To determine whether MT will produce greater improvements in mindfulness-related factors than SMT, and whether SMT will produce greater improvements in spinal stiffness than MT.

The primary analyses will employ the two-sample t-test to compare mean change in each specific mechanism to compare mean change in outcome from pre to post treatment between the two treatment arms. An overall, 2-sided, significance level of 0.05 will be used. Linear mixed models will be used as a supplemental analysis, allowing us to utilize all data collected, account for within subject variation, and model changes over time. The fixed effect part of the model will be

$Mechanism_{ij} = \beta_0 + \beta_1 Time_{ij} + \beta_2 Tx_i + \beta_3 (Tx_i * Time_{ij}) + \varepsilon_{ij}$ for subject i at visit j .

If β_3 is significantly negative ($p < .05$), this would indicate that the mechanism variable decreased more in SMT than in MT (Fitzmaurice, Laird, & Ware, 2011). In case of a significant interaction, we will test simple slopes of Time for each Treatment Condition separately AND by testing post treatment differences between MT and SMT controlling for pre-treatment values. As in Aim 1, we will follow this analysis with generalized linear mixed effects modeling (GLMM) with subject-specific intercepts and subject-specific slopes.

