In the absence of interactions, we will use linear mixed effects regression models to test the degree to which changes in non-specific and specific mechanisms account for unique and shared variance in pre-post outcome changes. More specifically, 0-order correlations among mechanism and outcome pre-post change scores will reveal “candidate” mechanisms (i.e., those with significant associations with pre-post outcome changes). We will use a series of hierarchical regressions to examine the degree to which ostensibly different mechanisms account for shared or unique variance in outcome changes. Such analyses will allow us to identify common areas of mechanism overlap (e.g., changes in self-efficacy and pain catastrophizing accounting for much shared variance in pain changes), and mechanism uniqueness (e.g., changes in spinal stiffness accounting for significant unique variance in pain changes even with other mechanism changes controlled).

Aim 4: Address competing causation pathways.

First, we will use an approach and techniques that we have used in previous publications [eg, [name], J.W., Nielson, W.R., Jensen, M.P., Heapy, A., Czlapinski, R., & Kerns, R.D. (2015). Specific and general therapeutic mechanisms in cognitive-behavioral treatment of chronic pain. *Journal of Consulting and Clinical Psychology*. 83, 1-11. PMID: 24979313]. Namely, we will test lagged and cross-

lagged effects using pre- to mid-treatment and mid- to post-treatment epochs. Given that endogenous opioid functioning will be assessed only at pre-and post-treatment, and given that the working alliance and subject expectations for benefit will be assessed only at 3- and 6-weeks, this approach will allow to examine comparable effects across all our specific and non-specific mechanisms. Residual change scores for all mechanism and outcome variables will be computed by regressing mid-treatment on pre-treatment values (i.e., a pre-mid residual change score), and regressing post-treatment on mid-treatment values (i.e., mid-post residual change score). For lagged relationships, regressions will be performed to identify the unique effect of pre-mid mechanism changes on mid-post outcome changes. This will require statistically controlling for the path from pre-mid mechanism change to mid-post mechanism change and pre-mid outcome change to mid-post outcome change. See Figure 1 and 2 below. The red line is the target lagged effect. The two blue lines are the paths to be controlled.

Figure 1

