[figure not shown]
[figure not shown]

Figure 2

For cross-lagged effects, the procedure will be inverted. Namely, we will test whether pre-mid changes in outcomes predict mid-post changes in mechanisms. Significant lagged effects paired with non-significant cross-lagged effects will add support to the notion that early-treatment changes in putative mechanisms influenced later-treatment changes in outcomes. In general, we expect that pre-mid changes in mindfulness and spinal stiffness will predict mid-post changes in pain interference (and other outcomes), but the inverse will not be the case.

Second, we will take a more fine-grained HLM approach using the weekly data. We will test whether: a) previous week levels of specific (e.g., mindfulness, spinal stiffness) and nonspecific mechanisms (e.g. self-efficacy) predict previous week to next week changes in outcomes; b) these relationships depend on time in treatment (i.e. quadratic trends could emerge indicating that early- vs late-treatment effects are distinct); c) whether the inverse relationships (i.e. outcomes predicting mechanisms) are also significant; d) whether patterns of lagged effects are different between MT and SMT. In general, we expect that previous week levels in mechanisms will predict previous week to current week changes in outcomes, and that the strength of these relationships will be strongest from Week 3 to Week 6 (when specific mechanisms have improved sufficiently to best affect improvements in outcomes).

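### For mindfulness, catastrophizing and self-efficacy, the supplemental mixed model's single linear Tx × Time slope runs through follow-up and is not the pre-post arm difference it is read as

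*Protocol*

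**What the plan says.** Section 9.6 makes the primary analysis for Aims 1 and 2 a two-sample t-test of mean pre-to-post change. It then adds a second model: "Linear mixed models will be used as a supplemental analysis, allowing us to utilize all data collected". The fixed part, printed identically under both aims, has an intercept, one Time coefficient, one treatment coefficient and one Tx × Time coefficient, β3. If β3 is significantly negative, "this would indicate that the mechanism variable decreased more in SMT than in MT". After a significant interaction, "we will test simple slopes of Time for each Treatment Condition separately", and the arms are also compared at post-treatment with adjustment for the pre-treatment value. The model has no visit indicators, knot or quadratic term, and it is not limited to the treatment phase. The unit of Time is not given.

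The target in section 9.5.2 is a pre-post quantity: "Secondary outcomes are pre-post treatment changes in mindfulness and spinal stiffness (specific mechanisms", with the non-specific mechanisms listed alongside. On timing, the précis and section 3 say: "Self-report mechanism and outcome variables will be assessed at baseline, 1-day after each weekly session", and again at 3 and 6 months. The schedule in 6.1 and the visit list in 6.2.5 confirm the follow-up assessments for mindfulness, catastrophizing and self-efficacy.

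**The concern.** A straight line makes the arms diverge at one constant rate from baseline to the last visit. If the difference builds up over eight sessions and then levels off or shrinks, no straight line fits it. On a calendar scale the two late visits largely set the slope, so β3 then mostly describes what happens between end of treatment and 6 months. The protocol nevertheless reads it as the treatment-phase result.

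Two things are at stake, both inside the supplemental analysis. The model can disagree with the primary t-test for a reason unrelated to the treatments. And because β3 must be significant before the baseline-adjusted post-treatment comparison is made, an attenuated β3 can suppress that comparison. For the two affected Aim 1 mechanisms (catastrophizing and self-efficacy), attenuation also leans toward the similarity that the protocol hypothesizes.

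**Working it through.** **Plan's own figure.** Section 9.2 gives Aim 2 power of 0.800 at d = 0.36 and 0.983 at d = 0.53 with 120 per arm. The noncentrality is 0.36 × √(120/2) = 2.79. The noncentral t gives 0.793 and the normal approximation 0.796. For d = 0.53 the noncentral t gives 0.983. Both stated values are reproduced closely.

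**Which mechanisms are affected.** Mindfulness, catastrophizing and self-efficacy have 11 occasions: baseline, eight sessions, 3 months and 6 months. Session 8 is their last treatment-phase value. The others have no 3- or 6-month data:

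- Endogenous opioid (EO) function: "Given that endogenous opioid functioning will be assessed only at pre-and post-treatment". With two occasions, β3 times the interval is exactly the pre-post arm difference.
- Conditioned pain modulation (CPM): pre- and post-treatment laboratory visits only, so the same holds.
- Spinal stiffness: sessions 1–8 only. Slope × range recovers 100% of the difference for a linear rise, and 94% if the plateau is reached at session 4.
- Working alliance and expectations: no assessment at follow-up.

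**What β3 estimates.** In complete balanced data with a random intercept, with or without a random slope, the fitted β3 is the least-squares slope of the arm-difference curve Δ(t):

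β3 = Σ(t − t̄)Δ(t) / Σ(t − t̄)²

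**Assumed times.** Weeks 0, 4–11, 25 and 38, which fit the stated 38-week course. Then t̄ = 123/11 = 11.18 and Σ(t − t̄)² = 1185.6, of which the two follow-up visits contribute 77%. On visit number 0–10, t̄ = 5 and the sum of squares is 110.

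**Assumed curves.** Δ is scaled to 1 at session 8. A gradual rise gains 1/8 per session. An immediate change reaches 1 at the first weekly survey.

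| Curve (share kept at 3 / 6 months) | Weeks: numerator → β3 × 11 | Visit number: numerator → β3 × 8 |
|---|---|---|
| Gradual, 100% / 100% | 29.32 → 27% | 12.0 → 87% |
| Gradual, 75% / 50% | 12.45 → 12% | 8.5 → 62% |
| Gradual, 50% / 0% | −4.41 → −4% | 5.0 → 36% |
| Immediate, 50% / 0% | −22.55 → −21% | −2.0 → −15% |

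For example, 29.32 / 1185.6 × 11 = 0.27. With weeks 0, 1–8, 21 and 34 instead, the four calendar values are 20%, 8%, −4% and −18%.

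**Illustrative power.** Assume d = 0.36 in units of the SD of change, outcome SD 1, within-person correlation 0.6 (residual variance 0.4), 120 per arm and a random intercept only. The true session-8 difference is 0.36 × √0.8 = 0.322. In weeks, SE(β3) = √(2 × 0.4 / 120 / 1185.6) = 0.00237. For the gradual, fully kept curve, z = 0.322 × 0.02473 / 0.00237 = 3.36.

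| Gradual curve | β3 significant, weeks | β3 significant, visit number | Session-8 contrast |
|---|---|---|---|
| Kept | 92% | 99.5% | 80% |
| Halved by 6 months | 30% | 89% | 80% |
| Faded to zero by 6 months | 8%, nearly all in the wrong direction | 47% | 80% |

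**The case against.** The strongest defence is that the model is labelled supplemental. The primary t-test estimates the pre-post contrast directly, is not gated by β3, and is what Aim 2 is powered on. A reader might infer that the trial could miss or reverse a real post-treatment effect. The documents do not support that, because the gate acts only within the supplement. Nor does the problem reach EO function, the primary mechanism outcome, or any other mechanism without follow-up data.

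The size of the error also depends on things the protocol does not give: the unit of Time and how much of the difference persists. A reader might quote a 73% chance that β3 is significant in the wrong direction. That figure needs divergence by the first weekly survey, complete loss by 6 months, calendar time and no random slope. It falls to about 53% with a random-slope SD of 0.54 over 38 weeks, and to about 11% on visit number without a random slope. It should not be presented as the expected result.

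It is also tempting to say that the protocol itself predicts a fading arm difference. Its remark that "quadratic trends could emerge indicating that early- vs late-treatment effects are distinct" concerns the Aim 4 lagged mechanism–outcome relationships. The passage in section 3 on separating immediate from longer-term effects concerns how mechanisms predict maintained outcomes. Neither describes arm differences in mechanisms.

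One could add that the time scale and analysis window are normally left to the SAP, and that section 9.6 promises residual checks and remedies. The first point stands for the time scale. However, the protocol has already written out the equation, the data set and the reading rule. The remedies it names, transformations and bootstrap standard errors, do not repair a wrongly shaped mean curve.

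**Conclusion.** The point holds for mindfulness, catastrophizing and self-efficacy in the supplemental model of Aims 1 and 2. Fitted as written to all visits, β3 is not the pre-post arm difference, and its sign is not a reliable statement of which arm changed more by end of treatment.

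For a gradual rise on a calendar scale, it implies about 27% of the session-8 difference at best and falls to about zero (−4%) if the difference fades. On visit number the distortion is milder, 87% down to 36%. A clear reversal appears in the main table only when change is immediate and then fades (−21% in weeks, −15% on visit number).

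These figures rest on assumed visit times, assumed retention curves and complete data. That β3 differs from the pre-post contrast unless the difference happens to grow linearly throughout does not depend on them. The consequence is limited to the supplement: it may fail to support or may contradict the primary t-test, and its gate may withhold the baseline-adjusted comparison. This is worth correcting, but it does not threaten the primary analyses or the sample size.

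**What to change.** For the three mechanisms with 3- and 6-month data, replace linear Time in section 9.6 with categorical visit. A piecewise-linear Time with a knot at end of treatment is an alternative if change is roughly linear within each phase. Name the Tx × visit contrast at session 8 against baseline as the supplemental pre-post effect, and report separate 3- and 6-month contrasts. For these mechanisms, remove the reading of the sign of β3, and do not make the baseline-adjusted post-treatment comparison depend on a significant β3. The other mechanisms need no change on this account.

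The cost is a few sentences and a few degrees of freedom. There is also some loss of power if a gradually arising difference is sustained: about 80% against 92% in the calendar case above, with a larger gap on visit number. In complete data, categorical visit recovers the session-8 difference in full whatever the shape of the curve.

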The first focus is to determine whether pre-post changes in specific and non-specific mechanisms (e.g., specific: spinal stiffness changes; non-specific: self-efficacy changes) interact with Treatment Condition to predict pre-post changes in DVs (e.g. pain intensity changes). A significant interaction would suggest that pre-post changes in a mechanism factor predicted pre-post changes in a DV **differently** depending on Treatment Condition. In the case of a significant interaction, we will test simple slopes of pre-post mechanism changes for DV changes for each Treatment Condition separately. We do not expect many significant interactions. Thus, we focus our power analyses on detecting increments in R^2 when adding pre-post mechanism change scores into regressions to predict pre-post changes in outcomes.

Multiple Regression Power Analysis

Power	N of independent variables teste	R ² for Independent Variable(s) tested	R ² for Variables controlled
0.74152	1	0.025	0.1
0.81731	1	0.030	0.1
0.79137	1	0.025	0.2
0.86115	1	0.030	0.2
0.84360	1	0.025	0.3
0.90403	1	0.030	0.3

All calculations assume $N=240$ and $\alpha=0.05$. Again note that we expect to recruit 286 subjects to achieve an analyzable sample of 240 completed subjects.

With 10% of variance in pre-post outcome changes accounted by mechanism variables already in the equation, we have 74% power to detect a 2.5% increment in R^2 with the addition of another mechanism variable. This increases to 90% power to detect a 3% increment in R^2 when mechanism variables already in the equation account for 30% of the outcome changes. Note that these power analyses for Aim 3 were based on testing the association between changes in EO function and changes in pain interference.

Treatment Assignment Procedures

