Aim 3: Test relative predictive validity of non-specific and specific mechanisms. The primary objective is to test to what degree changes in non-specific and specific mechanisms predict changes in pain, mood and function, and whether these relationships depend on the treatment received. We will first test Mechanism Change x Treatment interactions to determine whether changes in any candidate mechanisms predict outcomes to a greater degree in one treatment than the other. In the absence of interactions, which we expect to be largely the case, we will test the degree to which changes in non-specific and specific mechanisms account for unique and shared variance in predicting outcomes.

Aim 4: To address competing causation paths. The primary objective is to test lagged and cross-lagged effects of early-treatment changes in non-specific and specific mechanisms predicting late-treatment changes in outcomes. Analyses are described in detail above.

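### Aim 3, no-interaction step: candidate mechanisms are picked by zero-order significance in the same data, although the target is unique variance

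*Protocol*

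**What the plan says.** Aim 3 has two steps. The first tests Mechanism Change × Treatment interactions. The second applies when none is found, and Section 9.5 makes clear that this is the expected route: "In the absence of interactions, which we expect to be largely the case".

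For the second step, Section 9.6 names unique and shared variance in pre-post outcome change as the quantity of interest. It then becomes more specific: "0-order correlations among mechanism and outcome pre-post change scores will reveal" the candidate mechanisms, which it explains as "those with significant associations with pre-post outcome changes". The next sentence reads: "We will use a series of hierarchical regressions to examine the degree to which ostensibly different mechanisms account for shared or unique variance". The section's example of a unique mechanism is spinal stiffness "accounting for significant unique variance in pain changes even with other mechanism changes controlled".

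Section 9.2 gives the Aim 3 power for adding one mechanism to a regression, at N = 240 and alpha 0.05. At the low end, "we have 74% power to detect a 2.5% increment in R^2 with the addition of another mechanism variable", with 10% of variance already explained. At the high end, "This increases to 90% power to detect a 3% increment in" R², with 30% already explained. No preliminary screen appears in that calculation.

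**The concern.** The selection rule and the target differ. A zero-order correlation mixes a mechanism's own contribution with whatever it shares with the other mechanisms; unique variance removes the shared part. A mechanism can pass on shared variance alone, or fail although its unique contribution is real.

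Selection and estimation also use the same change scores in the same people. Weak mechanisms that pass tend to be those whose sample correlation came out high, so their estimates are biased upward, and ordinary p-values are not valid conditional on selection. Section 9.6 describes no separate sample, shrinkage or selection-adjusted inference for this step. For the covariates in Aims 1 and 2, by contrast, it chooses LASSO expressly to avoid the faults of stepwise selection.

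At stake are the size attached to weak mechanisms, the chance that a real one never reaches the joint model, and whether the stated increment power describes the procedure that will be run.

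**Working it through.** **Inputs.** N = 240, alpha = 0.05, increments of 0.025 and 0.030, and R² controlled of 0.10 to 0.30 (Section 9.2). The screening threshold is not stated; two-sided 0.05 is assumed. Correlations among mechanisms are not given; 0, .3 and .5 are assumptions.

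**1. The plan's own power.** With f² = ΔR²/(1 − ΔR² − R²c), noncentrality N·f², and 1 and 237 degrees of freedom (two predictors):
- ΔR² .025 over .10: f² = .025/.875 = .0286, noncentrality 6.86, power .7415 (stated 0.74152).
- ΔR² .030 over .30: f² = .030/.67 = .0448, noncentrality 10.75, power .9040 (stated 0.90403).

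The other four rows reproduce as well. All six are correct for a test with no screen.

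**2. Where the screen cuts.** Critical r = t/√(t² + N − 2) = 1.970/√(3.881 + 238) = .127.

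**3. Marginal overstatement after the screen (simulation).**

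| True r | Admitted | Mean r if admitted | Ratio to truth |
|---|---|---|---|
| .05 | 12% | .147 | 2.9 |
| .10 | 34% | .168 | 1.7 |
| .158 (2.5% of variance) | 68–69% | .190 | 1.2 |
| .20 | 88% | .213 | 1.07 |
| .30 | 99.7% | .299 | 1.00 |

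**4. Effect on the unique-variance test.** Take one other mechanism explaining R²c, with correlation ρ to the tested one. The tested mechanism's marginal correlation is then r = ±√ΔR²·√(1 − ρ²) + ρ·√R²c, where the minus sign is suppression. For ΔR² = .025, R²c = .10, ρ = .3:
- same direction: .1581 × .954 + .3 × .316 = .246;
- opposite sign: −.151 + .095 = −.056.

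Simulated results, where joint power means admitted and then significant in the regression:

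| Pattern, ΔR² .025 over .10 | Marginal r | Admitted | Joint power | Mean admitted semipartial r ÷ truth |
|---|---|---|---|---|
| Overlap, ρ = .3 | .246 | 97% | .74 | 1.02 |
| Overlap, ρ = .5 | .295 | 99.7% | .73–.74 | 1.00 |
| Uncorrelated | .158 | 69% | .66–.67 | 1.18 |
| Suppression, ρ = .3 | −.056 | 14–15% | .14 | 1.5 |
| Suppression, ρ = .5 | .021 | 6% | .01 | 0.6 |

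Without the screen the simulated partial test has power .73 to .74 in every row.

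For ΔR² .030 over .30 (stated .90), joint power is .90 with overlap and .75 if uncorrelated. Under suppression it is .03 at ρ = .3 and .38 at ρ = .5, so the loss is not monotone in ρ.

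**5. A masking example (assumed correlations).** Two mechanisms correlate .40 and .05 with the outcome and .50 with each other. The second has β = (.05 − .40 × .50)/(1 − .25) = −.20 and a unique share of .04 × .75 = .030. Its partial test has 84% power, but it passes the screen 12% of the time.

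**6. False positives.** For a mechanism with no unique effect, the chance of passing both steps is 2 to 4%, below the nominal 5%. Conditional on admission the picture depends on overlap. If it is uncorrelated with the rest, it is admitted 5% of the time and then significant 49% (R²c .30) to 72% (R²c .10) of the time. If it correlates .3 with the other mechanism, it is significant about 4 to 8% of the time once admitted.

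**The case against.** The strongest reply is that the protocol never says non-candidates are left out. The second step opens with an unrestricted statement about changes in specific and non-specific mechanisms, and Section 9.6 uses the word candidate for the full set at the interaction step, which is not screened. This stands in part. Exclusion is an inference, and it concerns only the second step. It is still the plain reading, because defining candidates by significance immediately before the regressions has no other stated purpose.

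The second reply is that the only dependence the protocol describes is same-direction overlap, such as self-efficacy and catastrophizing sharing much variance. There the screen costs essentially nothing. This stands. The severe losses need suppression, which the document does not suggest, and a suppressor whose adjusted sign runs against its marginal one is not obviously a missed therapeutic mechanism. The 1.7-fold figure at r = .10 concerns the marginal correlation, at 1% of variance, below what the plan is powered for. For unique effects of the planned size, the corresponding inflation is 0 to 2% with overlap and 18% if uncorrelated.

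A reader might also infer that the screen multiplies false positives or that the power table is wrong. Neither follows: the joint error rate per mechanism falls, and the table is arithmetically right for an unscreened test.

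**Conclusion.** The concern holds for the no-interaction step of Aim 3. As written, the step selects on a marginal correlation in the same data when the target is unique variance. It overstates weak effects, with negligible inflation at r of .30 or more, and it can drop a mechanism whose unique effect is masked.

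For the stated 2.5% increment over R² of .10, the power actually available runs from .74 (no loss) through .66 to .67 down to .14 or .01, according to correlations among mechanisms that the protocol does not give. The conclusion rests on reading the candidate rule as an entry rule and on a 0.05 screening threshold.

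It would go too far to say that the protocol expressly bars non-significant mechanisms, that all of Aim 3 is screened, or that the stated power fails in general. Aim 3 is a secondary objective, and the primary comparison of change in EO function is untouched.

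**What to change.** For pain interference, state that all prespecified mechanisms enter the regression whatever their zero-order significance. Report each mechanism's unique variance as its increment when entered last, so that it does not depend on order, and report shared variance alongside, both with bootstrap confidence intervals. Keep the zero-order correlations as description.

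EO function, CPM, catastrophizing, self-efficacy, mindfulness and spinal stiffness enter as pre-post change scores. Working alliance and expectations need their own rule, because the schedule in Section 6.1 and the visit list in Section 6.2.4 give neither a post-treatment measure. They can enter as the session 3 or session 6 level, or as the change between those sessions, with the choice fixed in advance.

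The cost is modest: about 8 to 10 predictors for 240 participants, depending on how many mindfulness measures are kept, and slightly wider intervals. No new data are needed. If the sponsor never meant to exclude non-candidates, one sentence saying so removes the entry problem.
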